### 9.2.5.2. Cohort Study

In the cohort study (Phase 2), depending on the safety outcome of interest, follow-up will begin on cohort entry or the day following cohort entry ([Table 2](#)) and extend until the earliest of:

- The occurrence of an outcome of interest ([Section 9.3.2](#));
- For COMIRNATY 2023-2024 Formula recipients, receipt of a COVID-19 vaccine other than the COMIRNATY 2023-2024 Formula; for comparators whose qualifying healthcare encounter is for a non-COMIRNATY 2023-2024 Formula COVID-19 vaccination, receipt of a different brand of COVID-19 vaccine from cohort entry;
- One year after cohort entry;
- Disenrollment from the health plan, death, or the end of data collection;

Those comparators who later receive a dose of COMIRNATY 2023-2024 Formula may be eligible for inclusion in the COMIRNATY 2023-2024 Formula cohort if they meet the eligibility criteria for cohort entry.

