### 9.3.1.2. Comparator Cohort

The Phase 2 cohort study will include comparators with no recorded vaccination for the COMIRNATY 2023-2024 Formula. To improve comparability with the COMIRNATY 2023-2024 Formula vaccinated cohort, patients included in the comparator cohort will be required to have a code indicative of a healthcare encounter, including one of the following:

- Presence of a code for a vaccine other than the COMIRNATY 2023-2024 Formula;
- Presence of a code indicative of an outpatient healthcare encounter.

Codes relating to other vaccines or outpatient visits are provided in [Annex 2 \(Appendix II\)](#).

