**Table 2. Clean periods and risk intervals for safety outcomes of interest**

Outcome	Clean Period*	Vaccine Risk Interval*	Care Setting**
Acute disseminated encephalomyelitis	Days -28 to -1	Days 0 to 21	IP
Anaphylaxis	Days -30 to -1	Days 0 to 1	IP, ED
Bell's palsy	Days -183 to 0	Days 1 to 42	IP, OP
Cerebral venous sinus thrombosis	Days -365 to 0	Days 1 to 28	IP, OP
Convulsions/seizures, non-febrile	Days -42 to -1	Days 0 to 21	IP, OP
Encephalomyelitis	Days -183 to 0	Days 1 to 42	IP
Glomerulonephritis	Days -365 to 0***	Days 1 to 42***	IP, OP
Guillain-Barré syndrome	Days -365 to 0	Days 1 to 42	IP-primary position only
Herpes zoster	Days -270 to 0	Days 1 to 30	IP, OP
Immune-mediated myositis	Days -365 to 0***	Days 1 to 28	IP, OP
Immune thrombocytopenia	Days -365 to 0	Days 1 to 42	IP, OP
Kawasaki disease	Days -365 to 0	Days 1 to 21	IP, OP
Multi inflammatory syndrome	Days -365 to 0	Days 1 to 42	IP, ED
Multiple sclerosis	Days -365 to 0	Days 1 to 42***	IP, OP
Myocardial infarction	Days -365 to 0	Days 1 to 28	IP
Myocarditis/pericarditis	Days -365 to 0	Days 1 to 21	IP, OP

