**Table 2. Clean periods and risk intervals for safety outcomes of interest**

Outcome	Clean Period*	Vaccine Risk Interval*	Care Setting**
Pulmonary embolism	Days -365 to 0	Days 1 to 28	IP, OP
Stroke, hemorrhagic	Days -365 to 0	Days 1 to 28	IP
Stroke, ischemic	Days -365 to 0	Days 1 to 28	IP
Transverse myelitis	Days -365 to 0	Days 1 to 42	IP, ED

\*Expressed in relation to the day of vaccination or cohort entry (Day 0). When more than one vaccine risk interval had been cited in the prior literature, the present risk interval was chosen from the prior literature using the following order of priority for all outcomes other than myocarditis/pericarditis: 1) CBER 2021; 2) the most frequently cited risk interval in prior literature; and 3) the shortest risk interval cited in prior literature. The risk interval for myocarditis/pericarditis was chosen based on [CBER 2022](#).

\*\*IP, Inpatient; ED, Emergency department visit; OP, Outpatient facility claims and professional/provider claims.

\*\*\*Could not be determined from the literature, so modeled after other outcome intervals in [CBER 2021](#).

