### 17.3. Appendix III – Safety Outcomes of Interest

All codes are ICD-10 diagnosis codes; all outcomes will be defined based on the presence of a single code unless otherwise specified. In order to qualify as an outcome, the outcome-specific codes must be identified during emergency department visits, inpatient hospitalizations, or outpatient visits, as detailed in [Table 2](#). Outpatient visits are defined through physician evaluation and management codes ([Section 17.2.3](#)).

\* Outcome codes marked with an asterisk are based on COVID-19 vaccine studies conducted as part of the FDA’s CBER BEST system.

- Acute disseminated encephalomyelitis (ADEM)\*
  - G04.00 – Acute disseminated encephalitis and encephalomyelitis, unspecified
- Anaphylaxis\*
  - T80.52XA – Anaphylactic reaction due to vaccination, initial encounter
  - T78.2XXA – Anaphylactic shock, unspecified, initial encounter
- Bell's palsy\*
  - G51.0 – Bell’s palsy
  - G51.8 – Other disorders of facial nerve
  - G51.9 – Disorder of facial nerve, unspecified
- Cerebral venous sinus thrombosis (CVST)
  - I67.6 – Nonpyogenic thrombosis of intracranial venous system
  - I63.6 – Cerebral infarction due to cerebral venous thrombosis, nonpyogenic
- Convulsions/seizures (non-febrile)
  - G40.001 – Localization-related (focal) (partial) idiopathic epilepsy and epileptic syndromes with seizures of localized onset, not intractable, with status epilepticus
  - G40.009 – Localization-related (focal) (partial) idiopathic epilepsy and epileptic syndromes with seizures of localized onset, not intractable, without status epilepticus
  - G40.011 – Localization-related (focal) (partial) idiopathic epilepsy and epileptic syndromes with seizures of localized onset, intractable, with status epilepticus
  - G40.019 – Localization-related (focal) (partial) idiopathic epilepsy and epileptic syndromes with seizures of localized onset, intractable, without status epilepticus
  - G40.101 – Localization-related (focal) (partial) symptomatic epilepsy and epileptic syndromes with simple partial seizures, not intractable, with status epilepticus

090177e1a5be86fe\Approved\Approved On: 19-Mar-2026 15:57 (GMT)

- G40.109 – Localization-related (focal) (partial) symptomatic epilepsy and epileptic syndromes with simple partial seizures, not intractable, without status epilepticus

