- G40.812 – Lennox-Gastaut syndrome, not intractable, without status epilepticus
- G40.813 – Lennox-Gastaut syndrome, intractable, with status epilepticus
- G40.814 – Lennox-Gastaut syndrome, intractable, without status epilepticus
- G40.821 – Epileptic spasms, not intractable, with status epilepticus
- G40.822 – Epileptic spasms, not intractable, without status epilepticus
- G40.823 – Epileptic spasms, intractable, with status epilepticus
- G40.824 – Epileptic spasms, intractable, without status epilepticus
- G40.89 – Other seizures
- G40.901 – Epilepsy, unspecified, not intractable, with status epilepticus
- G40.909 – Epilepsy, unspecified, not intractable, without status epilepticus
- G40.911 – Epilepsy, unspecified, intractable, with status epilepticus
- G40.919 – Epilepsy, unspecified, intractable, without status epilepticus
- G40.A01 – Absence epileptic syndrome, not intractable, with status epilepticus
- G40.A09 – Absence epileptic syndrome, not intractable, without status epilepticus
- G40.A11 – Absence epileptic syndrome, intractable, with status epilepticus
- G40.A19 – Absence epileptic syndrome, intractable, without status epilepticus
- G40.B01 – Juvenile myoclonic epilepsy, not intractable, with status epilepticus
- G40.B09 – Juvenile myoclonic epilepsy, not intractable, without status epilepticus
- G40.B11 – Juvenile myoclonic epilepsy, intractable, with status epilepticus
- G40.B19 – Juvenile myoclonic epilepsy, intractable, without status epilepticus
- R56.1 – Post traumatic seizures
- R56.9 – Unspecified convulsions

- Encephalomyelitis\*
  - G04.02 – Postimmunization acute disseminated encephalitis, myelitis, and encephalomyelitis
  - G04.00 – Acute disseminated encephalitis and encephalomyelitis, unspecified
  - G04.81 – Other encephalitis and encephalomyelitis
  - G04.90 – Encephalitis and encephalomyelitis
  - G05.3 – Encephalitis and encephalomyelitis in diseases classified elsewhere
- Glomerulonephritis
  - N06.A Isolated proteinuria with C3 glomerulonephritis
  - N06.7 Isolated proteinuria with diffuse crescentic glomerulonephritis
  - N06.5 Isolated proteinuria with diffuse mesangiocapillary glomerulonephritis
  - N06.4 Isolated proteinuria with diffuse endocapillary proliferative glomerulonephritis
  - N04.A Nephrotic syndrome with C3 glomerulonephritis
  - N04.2 Nephrotic syndrome with diffuse membranous glomerulonephritis
  - N04.7 Nephrotic syndrome with diffuse crescentic glomerulonephritis

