#### **17.4.1.10. Neurological or Neurodevelopmental Conditions**

##### **17.4.1.10.1. ICD-10-CM Codes**

F70	Mild intellectual disabilities
F71	Moderate intellectual disabilities
F72	Severe intellectual disabilities
F73	Profound intellectual disabilities
F78	Other intellectual disabilities
F79	Unspecified intellectual disabilities
F80.0	Phonological disorder
F80.1	Expressive language disorder
F80.2	Mixed receptive-expressive language disorder
F80.4	Speech and language development delay due to hearing loss

- F80.81 Childhood onset fluency disorder
- F80.82 Social pragmatic communication disorder
- F80.89 Other developmental disorders of speech and language
- F80.9 Developmental disorder of speech and language, unspecified
- F81.0 Specific reading disorder
- F81.2 Mathematics disorder
- F81.81 Disorder of written expression
- F81.89 Other developmental disorders of scholastic skills
- F81.9 Developmental disorder of scholastic skills, unspecified
- F82 Specific developmental disorder of motor function
- F84.0 Autistic disorder
- F84.2 Rett's syndrome
- F84.3 Other childhood disintegrative disorder
- F84.5 Asperger's syndrome
- F84.8 Other pervasive developmental disorders
- F84.9 Pervasive developmental disorder, unspecified
- F89 Unspecified disorder of psychological development

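### In the Phase 2 cohort, a comparator's qualifying office visit can itself be counted as an incident seizure on Day 0, which biases the seizure rate ratio downward by an amount the protocol cannot fix

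*Protocol*

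**What the plan says.** - **Start of follow-up (9.2.5.2).** In the cohort, "follow-up will begin on cohort entry or the day following cohort entry", by reference to Table 2. Follow-up ends at the first outcome, at one year, or at other censoring.
- **Seizure row (Table 2).** "Convulsions/seizures, non-febrile Days -42 to -1 Days 0 to 21 IP, OP". The footnote counts days from vaccination or cohort entry, so Day 0 applies to comparators too.
- **Comparator entry (9.2.3, 9.3.1.2).** The entry date is that of the qualifying encounter. One of the two qualifying routes is "Presence of a code indicative of an outpatient healthcare encounter", identified by the evaluation and management (E/M) codes in 17.2.3.
- **Outpatient outcomes (17.3).** "Outpatient visits are defined through physician evaluation and management codes", with a pointer to the same 17.2.3 list. One diagnosis code is enough unless stated otherwise.
- **Seizure codes (17.3).** The list includes chronic epilepsy codes such as "G40.909 – Epilepsy, unspecified, not intractable, without status epilepticus".
- **Exclusion (9.2.2.2, 9.7.2.1).** People with the outcome in its clean period are removed after matching. For seizures that period stops on Day -1.

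**The concern.** The event that brings a comparator into the cohort can also be the outcome. A patient with established epilepsy who attends a check-up, with no seizure code in the previous 42 days, enters on that visit and has a seizure event the same day.

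The two arms are not equally open to this. A comparator who enters through a visit has an E/M claim on Day 0 by construction. A vaccinee enters on a vaccine code, which may be a pharmacy claim, and has an E/M claim that day only if the dose coincided with a visit. Day 0 events therefore tend to accumulate in the comparator arm and pull the rate ratio below its true value. In a safety study that is the unhelpful direction.

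**Working it through.** **1. Is the overlap specific to seizures?** Table 2 lists 20 outcomes. Seventeen have a clean period that includes Day 0 and an interval from Day 1. The three with a Day 0 start are ADEM (inpatient), anaphylaxis (inpatient, emergency department) and seizures (inpatient, outpatient). Only seizures join a Day 0 start to an outpatient setting.

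**2. Does anything planned remove the event?** The clean period does not reach Day 0. Propensity matching uses baseline data and cannot delete a Day 0 event. The covariate list headed "Neurological or Neurodevelopmental Conditions" (17.4.1.10) holds only F70 to F89 codes, so it does not capture epilepsy. The comparator-subset analyses in 9.7.2.3 may reveal the problem, but the primary ratio in 9.7.2.2 pools all matched comparators.

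**3. Size.** The protocol gives no seizure rate, no share of visit-entry comparators and no share of vaccinees with a same-day visit. There is no figure to reproduce, and every input below is an assumption. The true ratio is set to 1.

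*Additive model*, in which each Day 0 code is an extra event:

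RR = (L·T + f·q) / (L·T + s·q)

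L is the coded rate from Day 1 (2 to 10 per 1,000 person-years) and T is 1 year. s is the share of comparators entering by a visit (0.3 to 0.9), and f is the share of vaccinees with a visit on Day 0 (0 to 0.2). q is the chance that such a visit carries a seizure code with none in the prior 42 days (0.05% to 0.5%).

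- Middle case, L = 0.005, s = 0.7, q = 0.002: f = 0 gives 0.0050/0.0064 = 0.78; f = 0.2 gives 0.0054/0.0064 = 0.84.
- Lowest, L = 0.002, s = 0.9, q = 0.005, f = 0: 0.0020/0.0065 = 0.31.
- Highest, L = 0.010, s = 0.3, q = 0.0005, f = 0.2: 0.01010/0.01015, which rounds to 1.00.

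*First-event model*, in which patients with epilepsy would mostly have been counted later in the year anyway:

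- Vaccinees: A = e(1 − exp(−v)) + b
- Comparators: B = d + (e − d)(1 − exp(−v)) + b
- RR is about A/B, since at most about 1.3% of people have an event and person-time is nearly equal.

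e is the epilepsy prevalence, equal in both arms (0.5% to 1%), and v is coded visits per year (2 to 4). b is the background (50 to 300 per 100,000), and d is the share of comparators with a Day 0 code (0.06% to 0.45%). Vaccinees' same-day visits are set to zero.

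- Lowest, e = 0.005, v = 2, b = 0.0005, d = 0.0045: A = 0.005 × 0.8647 + 0.0005 = 0.004823; B = 0.0045 + 0.0005 × 0.8647 + 0.0005 = 0.005432; RR = 0.89.
- Highest, e = 0.01, v = 4, b = 0.003, d = 0.0006: A = 0.012817; B = 0.012828; RR = 1.00.
- Sensitivity: the lowest case with one visit a year instead of two gives 0.003661/0.005316 = 0.69.

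**4. After removing Day 0.** In the additive model both Day 0 terms vanish and RR = 1.00 in every scenario. In the first-event model, starting on Day 1 while keeping everyone gives B = A, so again 1.00. Excluding people with a Day 0 code as well leaves comparators at C = [(e − d)(1 − exp(−v)) + b]/(1 − d). In the highest case A/C = 0.012817/0.012235 = 1.05. In the lowest it is 0.004823/0.000937 = 5.15, but there 90% of comparators with epilepsy (0.45/0.5) enter on an epilepsy visit, a deliberately extreme corner. This overshoot bears on how the fix is reported.

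**The case against.** The strongest reply concerns size. Follow-up stops at the first event and a 42-day clean period leaves established epilepsy in both arms, so most Day 0 events are brought forward rather than added. The additive model therefore overstates the bias, and it is stronger still if same-day visits among vaccinees are set to zero. This stands. The first-event range of 0.89 to 1.00 is the fairer illustration under equal prevalence, although fewer visits per patient would lower it. More epilepsy among visit-selected comparators would lower it too, but that is a prevalence imbalance, not a Day 0 effect.

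The protocol also has partial safeguards: the comparator-subset analyses (9.7.2.3), empirically chosen covariates (9.3.3) and the option of an outcome-specific propensity model (9.7.2.1). They may expose or lessen imbalance, but none takes a Day 0 event out of the primary estimate.

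Three stronger readings are tempting and not supported.

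- **A far larger bias over Days 0 to 21.** The cohort is followed for up to one year. Section 9.2.5.2 uses Table 2 to set the start of follow-up, and 9.3.2.1 ties the risk and control intervals to the self-controlled risk interval (SCRI) design. No 22-day cohort ratio is planned.
- **An SCRI biased the opposite way.** The SCRI has no comparator arm, so this mechanism does not operate there. An epilepsy code at an office vaccination visit would be a different mechanism, and the protocol does not give the share of doses given at visits.
- **ADEM shares the defect.** It is inpatient only, so an outpatient entry visit cannot be the ADEM outcome.

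**Conclusion.** The defect is in the definitions. For seizures alone, a comparator's entry visit can be the outcome, and no provision removes it from the primary rate ratio. The direction is downward provided Day 0 visits are commoner among comparators and are about as likely to carry a seizure code in either arm. The entry rule makes the first condition likely, but the documents do not prove it.

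The size is unknown. Over one year it runs from negligible to material, depending on epilepsy prevalence, visit frequency and vaccinees' same-day visits, all of which are assumed here. It affects one of 20 outcomes.

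**What to change.** **Main change.** For the cohort seizure analysis, run the clean period through Day 0 and start follow-up on Day 1 in both arms, as 17 other outcomes already do. At minimum, exclude anyone in either arm whose Day 0 outpatient E/M claim carries a listed seizure code.

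**Report alongside it.** The Day 1 start is what removes the Day 0 events. The added exclusion falls mainly on comparators and can thin out epilepsy in that arm (step 4 of the working). Give the number excluded in each arm, and show the ratio with a Day 1 start but no Day 0 exclusion. If the two differ materially, established epilepsy is driving the result and the ratio should be read accordingly.

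**Cost.** Edits to the seizure row of Table 2, as it applies to the cohort, and to 9.2.5.2. Outcome-specific exclusions are applied after matching (9.7.2.1), so no rematching is needed, but the matching weights should be computed on the set that remains. True Day 0 convulsions leave the cohort analysis. They stay in the SCRI, whose Day 0 rule should be left unchanged. A longer seizure clean period, or epilepsy codes in the propensity score, are separate and more debatable changes; the second would mean refitting the score behind the single master cohort.

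**Separately.** Section 9.2.5.1 limits the Day 0 start to anaphylaxis and seizures, while Table 2 also gives ADEM an interval of Days 0 to 21. The two need reconciling.

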## 6. MILESTONES

Milestone	Planned Date
Final study protocol	31 March 2024
Registration in the HMA-EMA Catalogues of RWD	To be determined
Start of data collection a	15 January 2024
Interim report b	30 June 2024
End of data collection c, d	31 August 2025
Final study report d	30 April 2026

a For studies with secondary data collection, the start of data collection is defined as the planned date for starting data extraction for the purposes of the interim analysis.

b The milestone date was chosen to inform decision making for the next adapted vaccine before Fall 2024. To meet this milestone, the data extraction for the interim reporting will include data through 15 January 2024.

c For studies with secondary data collection, the end of data collection is defined as the planned date on which the analytical dataset will be first completely available; the analytic dataset is the minimum set of data required to perform the statistical analysis for the final reporting.

d The sponsor may extend the study period. This revision, if needed, will be communicated to the FDA as a protocol amendment. Details on this contingency plan are provided in [Section 9.2](#).

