### 9.1.2. Cohort Design

Phase 2 will consist of a propensity score-matched cohort study of individuals with and without a recorded dose of the COMIRNATY 2023-2024 Formula, conducted within the ORD. During the accrual period of 11 September 2023 through 31 March 2024, individuals who receive the COMIRNATY vaccine will be classified as exposed, and those with no recorded vaccination with the COMIRNATY 2023-2024 Formula but who have a healthcare encounter will be classified as comparators. Propensity score matching will be performed to address control of potential confounding, with matching to be conducted within age group and calendar periods. Age group will be defined as: 6 months–4 years; 5–11 years; 12–17 years; 18–64 years; and  $\geq 65$  years, while calendar periods will be defined by 14-day increments (e.g., 01 September 2023 to 14 September 2023, 15 September 2023 to 28 September 2023). Alternate calendar periods (e.g., one month) may be empirically explored. Thus, within any given calendar period, comparators within the same age group will be matched without replacement to a COMIRNATY recipient on PS, down to a maximum allowable level of precision in the PS ([Section 9.7.2.1](#)). This will ensure a sufficient pool of comparators for stratified and/or subpopulation analyses ([Sections 9.7.2.3 & 9.7.2.4](#)).

These matched cohorts will be followed for up to one year for occurrence of safety outcomes. For this Phase 2 matched cohort study, the safety outcomes of interest are listed in [Section 9.3.2](#).

090177e1a5be86fe\Approved\Approved On: 19-Mar-2026 15:57 (GMT)

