#### **9.7.2.3. Secondary Analysis**

The main analysis will compare the occurrence of safety outcomes in the COMIRNATY 2023-2024 Formula-exposed group to that of the matched comparator group. Secondary analyses will conduct this comparison separately, including recalculation of the matching ratio and accounting for individuals who are included in both study cohorts for various subsets of the matched comparator group, including:

- Comparators who, on cohort entry, received a 2023-2024 formulation of a COVID-19 vaccine other than COMIRNATY (i.e., Moderna or Novavax)
- Comparators who received a non-COVID-19 vaccine on cohort entry
- Comparators who did not receive a vaccine on cohort entry but had another type of outpatient health encounter.

090177e1a5be86fe\Approved\Approved On: 19-Mar-2026 15:57 (GMT)

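### Section 9.2.5.2 ends follow-up at a new formula for COMIRNATY recipients but only at a new brand for Moderna/Novavax comparators, which modestly biases the brand contrast if the next-season dose carries short-term risk

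*Protocol*

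**What the plan says.** One bullet in Protocol 9.2.5.2 holds both stopping rules. The first half reads "For COMIRNATY 2023-2024 Formula recipients, receipt of a COVID-19 vaccine other than the COMIRNATY 2023-2024 Formula". The second half, for comparators whose qualifying encounter was another COVID-19 vaccination, reads "receipt of a different brand of COVID-19 vaccine from cohort entry".

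The comparators in question are those of the first secondary analysis in 9.7.2.3: "Comparators who, on cohort entry, received a 2023-2024 formulation of a COVID-19 vaccine other than COMIRNATY", that is, Moderna or Novavax. They also form part of the pooled comparator group of the primary analysis (9.3.1.2, 9.7.2.2).

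Follow-up is capped at "One year after cohort entry" (9.2.5.2). Section 9.1.2 fixes entry: "During the accrual period of 11 September 2023 through 31 March 2024". The Milestones table (Section 6) puts the end of data collection at 31 August 2025, and its footnote says that the interim date was chosen "to inform decision making for the next adapted vaccine before Fall 2024".

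**The concern.** The first rule turns on the formula and the second on the brand. Suppose two matched people enter in December 2023 and each takes their own brand's new formula in October 2024. The COMIRNATY recipient is censored on that day. The Moderna recipient stays in, and events after the new dose are counted in the 2023-2024 Moderna group.

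Two things follow for the brand contrast. Any short-term risk after the second dose enters the comparator rate only. Late COMIRNATY person-time also comes only from people who have not been revaccinated with a new formula, while the comparator side keeps its same-brand revaccinators. In a post-authorization safety study, an asymmetry that tends to favour the study product should be removed when this can be done cheaply.

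**Working it through.** **1. Does the text allow one common reading?** Section 9.3.3 uses brand and 2023-2024 formulation as separate terms when it describes prior COVID-19 vaccination. Section 9.7.2.3 and the heading of 17.2.1 define the other COVID-19 vaccines by their 2023-2024 formulation. The self-controlled stopping rule in 9.2.5.1 is also worded by formula. The brand clause is the exception, and no other section reconciles the two. A repeat dose of the same 2023-2024 product stops neither group, and a switch of brand stops both. The gap concerns only next-season doses of the same brand.

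**2. Does follow-up reach the next season?** The documents give no launch date, so it is assumed here. Share of the follow-up year after launch = max(0, entry + 365 days − launch) / 365.

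| Entry | Launch 1 Sep 2024 | 22 Sep 2024 | 15 Oct 2024 |
|---|---|---|---|
| 11 Sep 2023 | 9/365 = 2.5% | 0% | 0% |
| 15 Oct 2023 | 43/365 = 11.8% | 22/365 = 6.0% | 0% |
| 15 Dec 2023 | 104/365 = 28.5% | 83/365 = 22.7% | 60/365 = 16.4% |
| 31 Mar 2024 | 211/365 = 57.8% | 190/365 = 52.1% | 167/365 = 45.8% |

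The share of accrual days with any overlap is 100%, 94% and 82% for the three launch dates. If entry were uniform over accrual (assumed), the mean overlap would be 30%, 24% and 19%.

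**3. How large is the effect?** The plan gives no figure to reproduce. Let both vaccines have the same true effect, so that the correct ratio is 1.00. Let L be the risk window in days, R the in-window rate ratio, p the share taking their own brand's new formula, and t the day of that dose. Table 2 of the protocol supplies L: 2 days for anaphylaxis, 21 for myocarditis/pericarditis, 28 for myocardial infarction, pulmonary embolism and stroke, and up to 42 for others. R, p and t are assumed.

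- COMIRNATY: Tc = (1 − p)·365 + p·t; rate = (Tc + (R − 1)L) / Tc.
- Comparator: rate = (365 + (R − 1)L + p(R − 1)·min(L, 365 − t)) / 365.

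With L = 42, R = 3, p = 0.3, t = 300: Tc = 345.5. The COMIRNATY rate is 429.5/345.5 = 1.243, the comparator rate is (365 + 84 + 25.2)/365 = 1.299, and the ratio is 0.957. All results at R = 3, t = 300:

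| L (days) | p = 0.3 | p = 0.5 |
|---|---|---|
| 2 | 0.997 | 0.996 |
| 21 | 0.976 | 0.961 |
| 28 | 0.969 | 0.950 |
| 42 | 0.957 | 0.931 |

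A separate set of assumptions (dose at day 290, p from 0.2 to 0.6, L of 21 or 42, R of 2 or 3) gives ratios of 0.92 to 0.99, with COMIRNATY person-time at 0.88 to 0.96 of the comparator's.

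**4. When does it vanish or reverse?** With R = 1 both rates equal 1 and the ratio is 1.00. If only the first dose carries risk, the last term of the comparator rate drops out. For L = 42, R = 3 the ratio is then 1.243/1.230 = 1.01 (p = 0.3) or 1.253/1.230 = 1.02 (p = 0.5), because early censoring spreads the first-dose excess over less COMIRNATY person-time. With the same stopping rule in both groups the ratio returns to 1.00.

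**The case against.** Several counter-arguments have force.

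- **Wording.** The COMIRNATY clause could be meant as any other manufacturer's vaccine, much as similar words serve for same-day receipt in 9.2.1.2 and 9.2.2.2. Both halves would then be brand rules. The literal reading remains the more natural one, and the ambiguity itself needs settling.
- **Coding.** A reader might infer that every next-season COMIRNATY dose will in fact be censored. The documents do not support that. The CPT descriptors in 17.1.1 give a dose strength and no season, so a dose billed only under those codes may be classed as the 2023-2024 Formula and stop nothing. The realised asymmetry may be smaller than the text implies. This leaves the formula clause hard to apply; it does not make the two rules equal.
- **Size.** Uptake and launch date are not in the documents. Most Table 2 windows are shorter than 42 days. Day 300 cannot occur before 6 November 2023 entry if launch is 1 September 2024. Section 9.2 expects uptake to have levelled off by the end of March, so the 58% overlap describes what are probably few late entrants. With R = 10 and a 42-day window the formula gives 0.84 to 0.89, but no listed outcome is tied to a tenfold rate sustained for 42 days, so those figures should not be relied on.
- **Reach.** Shifts of this size will rarely decide whether the signal threshold in 9.3.2 (rate ratio above 3.0 with P below 0.01) is crossed. Moderna/Novavax entrants are also one of three comparator types.
- **Completeness.** Section 9.2.5.2 names no COVID-19-vaccine stopping rule for comparators who enter on a non-COVID-19 vaccine or an outpatient visit. Aligning the two clauses does not close that separate gap in the primary comparison.

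**Conclusion.** The two stopping rules differ as written, and follow-up extends far enough for the difference to matter. The effect is clearest in the secondary brand contrast. It is diluted in the pooled primary analysis by an unknown share, for which no figure can be given.

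The bias is conditional and modest. If the next-season dose raises short-term risk, the ratio falls to about 0.93 to 0.98 for windows of 21 to 42 days, given R = 3, 30-50% same-brand uptake and a dose at day 300. For anaphylaxis it is about 0.996 to 0.997. Without a vaccine effect there is no bias through this mechanism, and if only the first dose carries risk the direction reverses slightly.

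A reader might conclude that the asymmetry materially distorts the primary result or hides a safety signal. The documents do not support either conclusion. The point is worth correcting because the contrast in 9.7.2.3 should treat its two groups alike and no reason is given for treating them differently.

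**What to change.** Replace the two halves of the bullet in 9.2.5.2 with one mirror-image clause: recipients of any 2023-2024 COVID-19 vaccine end follow-up at receipt of any COVID-19 vaccine other than the 2023-2024 product received at cohort entry.

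State how next-season doses are recognised and apply it identically in both groups: by NDC where present, otherwise by a stated changeover date after which a same-brand claim counts as a new formula. The date is needed because the CPT descriptors for COMIRNATY (17.1.1), Moderna (17.2.1.1.1) and Novavax (17.2.1.2.1) carry no season.

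This version is dated 18 March 2026 and the final report is planned for 30 April 2026. If the primary programs are already fixed, run the symmetric rule as a sensitivity analysis for the brand contrast and report how many comparators it affects.

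The cost is some late comparator person-time, a changeover date that has to be defined and justified, the matching programming, and an amendment with the ethics review described in 10.3 if the main rule is changed.
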